8.3.1.1. Adverse Event Monitoring with a Systematic Questionnaire

Before administering the C-SSRS or the PHQ-9, study site personnel will question the participant about any change in the preexisting condition(s) and the occurrence and nature of any AEs.

Nonserious AEs obtained through the questionnaire are recorded and analyzed separately. Only *serious* AEs elicited through the C-SSRS or PHQ-9 are to be recorded as AEs via the eCRF and reported to Lilly or its designee within 24 hours as SAEs. For this study, the C-SSRS is adapted for the assessment of the ideation and behavior categories only. The Intensity of Ideation and Lethality of Behavior sections are removed.

The C-SSRS is a scale that captures the occurrence, severity, and frequency of suicidal ideation and/or behavior during the assessment period. The scale includes suggested questions to solicit the type of information needed to determine if suicidal ideation and/or behavior occurred. The tool was developed by the National Institute of Mental Health trial group for the purpose of being a counterpart to the Columbia Classification Algorithm of Suicide Assessment categorization of suicidal events.

The PHQ-9 is a validated self-report screening tool that assesses the presence and intensity of depressive symptoms. The PHQ-9, which incorporates the 9 Diagnostic and Statistical Manual-IV depression criteria as “0” (not at all) to “3” (nearly every day), was developed for use in primary care settings (Kroenke et al. 2001).

8.3.2. Follow-up of AEs and SAEs

After the initial AE or SAE report, the investigator is required to proactively follow each participant at subsequent visits/contacts. All SAEs will be followed until resolution, stabilization, the event is otherwise explained, or the participant is lost to follow-up (as defined in Section 1.3).

8.3.3. Regulatory Reporting Requirements for SAEs

- Prompt notification by the investigator to the Sponsor of a SAE is essential so that legal obligations and ethical responsibilities towards the safety of participants and the safety of a study intervention under clinical investigation are met.
- The Sponsor has a legal responsibility to notify both the local regulatory authority and other regulatory agencies about the safety of a study intervention under clinical investigation. The Sponsor will comply with country-specific regulatory requirements relating to safety reporting to the regulatory authority, Institutional Review Boards (IRB)/Independent Ethics Committees (IEC), and investigators.

- Investigator safety reports must be prepared for SUSARs according to local regulatory requirements and sponsor policy and forwarded to investigators as necessary.
- An investigator who receives an investigator safety report describing an SAE or other specific safety information (for example, summary or listing of SAEs) from the Sponsor will review and then file it along with the IB and will notify the IRB/IEC, if appropriate according to local requirements.

8.3.4. Pregnancy

- Details of all pregnancies in female participants and female partners of male participants will be collected after the start of study intervention and the participant will be followed to determine the outcome of the pregnancy for mother and neonate.
- If a pregnancy is reported, the investigator should inform the Sponsor within 24 hours of learning of the pregnancy and should follow the procedures outlined in Section 10.4 (Appendix 4).
- Abnormal pregnancy outcomes (for example, spontaneous abortion, fetal death, stillbirth, congenital anomalies, and ectopic pregnancy) are considered SAEs.

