7.2. Participant Discontinuation/Withdrawal from the Study

To minimize the amount of missing data and to enable assessment of study objectives as planned in the study protocol, every attempt will be made to keep participants in the study irrespective of the following:

- adherence to or discontinuation from study drug
- adherence to visit schedule
- missing assessments
- study drug discontinuation due to AE
- development of comorbidities
- development of clinical outcomes

The circumstances listed above are *not* valid reasons for discontinuation from the study.

[figure not shown]
Participants will be withdrawn from the study in the following circumstances:

- enrollment in any other clinical study involving an IP or enrollment in any other type of medical research judged not to be scientifically or medically compatible with this study
- participation in the study needs to be stopped for medical, safety, regulatory, or other reasons consistent with applicable laws, regulations, and good clinical practice (GCP)
- participant requests to be withdrawn from the study and clearly indicates that there will be no further contact of any kind with the site
- Female participants will be withdrawn from the study if the participant becomes pregnant.

Participants who agree to provide information relevant to any trial endpoint at the end of the study are not considered to have discontinued from the study.

[figure not shown]
Participants discontinuing from the study prematurely for any reason should complete AE and other safety follow-up per Section 1.3 (Schedule of Activities), Section 8.3 (Adverse Events and Serious Adverse Events), and Section 8.2 (Safety Assessments) of this protocol.

7.2.1. Participant Disposition and Timing of Safety Follow-up for the Primary Endpoint (72 Weeks)

Abbreviations: ED = early discontinuation of treatment; Pt = participant; wks = weeks.

7.2.2. Participant Disposition and Timing of Safety Follow-up for those with Prediabetes at Randomization Continuing in Additional 2-year Treatment Period

Abbreviations: ED = early discontinuation of treatment; wks = weeks.

Note: Participants with prediabetes at randomization who discontinue study drug on or before Week 72 are not eligible to continue in additional 2-year treatment period after Visit 21 (Week 72) and should proceed to V801.

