- After obtaining the necessary signed informed consent from the pregnant female partner directly, the investigator will record pregnancy information on the appropriate form and submit it to the Sponsor within 24 hours of learning of the partner's pregnancy. The female partner will also be followed to determine the outcome of the pregnancy. Information on the status of the mother and child will be forwarded to the Sponsor. Generally, the follow-up will be no longer than 6 to 8 weeks following the estimated delivery date. Any termination of the pregnancy will be reported regardless of fetal status (presence or absence of anomalies) or indication for the procedure.

Female Participants who become pregnant

- The investigator will collect pregnancy information on any female participant who becomes pregnant while participating in this study. Information will be recorded on the appropriate form and submitted to the Sponsor within 24 hours of learning of a participant's pregnancy.
- The participant will be followed to determine the outcome of the pregnancy. The investigator will collect follow-up information on the participant and the neonate and the information will be forwarded to the Sponsor. Generally, follow-up will not be required for longer than 6 to 8 weeks beyond the estimated delivery date. Any termination of pregnancy will be reported, regardless of fetal status (presence or absence of anomalies) or indication for the procedure.
- While pregnancy itself is not considered to be an AE or SAE, any pregnancy complication or elective termination of a pregnancy will be reported as an AE or SAE. A spontaneous abortion is always considered to be an SAE and will be reported as such. Any poststudy pregnancy-related SAE considered reasonably related to the study intervention by the investigator will be reported to the Sponsor as described in Section 8.3.2. While the investigator is not obligated to actively seek this information in former study participants, he or she may learn of an SAE through spontaneous reporting.

- Any female participant who becomes pregnant while participating in the study will discontinue study intervention and be withdrawn from the study.

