 - the “hybrid” estimand, is the average treatment effect of tirzepatide relative to placebo at 176/193 weeks, as an adjunct to a reduced-calorie diet and increased physical activity, for the randomized participants with prediabetes at randomization regardless of the adherence to treatment

End of study participation for a participant will be the earliest of date of death, date of withdrawal from further participation in the study, or date of safety follow-up visit (Visit 801 or Visit 802). For participants considered to be lost-to-follow-up, end of study participation will be the date of lost-to-follow-up reported by the investigator. Participant data included in the database after the last date of study participation (including safety follow-up period) will be excluded from statistical analysis.

Statistical treatment comparisons will only be performed between tirzepatide and placebo. Since the trial is not adequately powered to detect difference among tirzepatide doses, comparisons among tirzepatide doses will not be performed unless otherwise specified.

Statistical summaries and results of statistical analyses will be displayed in the following order: Placebo, tirzepatide 5 mg, tirzepatide 10 mg, tirzepatide 15 mg, and pooled tirzepatide (10 mg and 15 mg, or all doses combined, if necessary).

Not all analyses described in this SAP will necessarily be included in the Clinical Study Reports (CSRs). Any analysis described in this SAP and not provided in the CSR would be available upon request. Not all displays will necessarily be created as a “static” display. Some may be incorporated into interactive display tools instead of or in addition to a static display.

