6.14. Safety Analyses

Unless specified otherwise, safety assessments will be based on the SS (Table GPHK.6.1). All events that occur between the first dose date of study drug and the end date of study participation will be included, regardless of the adherence to study drug.

The statistical assessment of homogeneity of the distribution of categorical safety responses between tirzepatide doses and placebo will be conducted using Fisher's exact test, unless specified otherwise.

For selected continuous safety parameters, the mean change from baseline differences vs. placebo will be assessed via a MMRM using REML. Data from scheduled visits will be utilized for this analysis. Unless specified otherwise, the model for the analysis during 72 weeks treatment period will include country/pooled country, sex, prediabetes status at randomization, treatment group, visit and treatment-by-visit interaction as fixed effects, and baseline value of the safety parameter as a covariate. For the analysis during the 176 weeks treatment period (or 193 weeks), only participants with prediabetes at randomization in the SS will be included, and the model will contain the terms of country/pooled country, sex, treatment group, visit and treatment-by-visit interaction as fixed effects, and baseline value of the safety parameter as a covariate. To model the covariance structure within participants, the unstructured covariance matrix will be used. If this model fails to converge, the covariance structures specified in Section 6.13.1.1 will be tested in order until met convergence. If the data does not warrant the MMRM model, then ANCOVA model will be conducted.

For selected safety parameters, time-to-first-event analysis via the Cox-proportional hazards model may be conducted. Participants without the event will be censored at the end of study participation. For participants experiencing the event, the "time-to-first-event" will be the time (in days) from first dose to first occurrence of the event.

Where necessary, the rate of events will be analyzed using a generalized linear mixed-effects model assuming the number of events follow a negative binomial distribution and with treatment as a fixed effect. The logarithm of days during the active treatment period will be adjusted as an offset to account for possible unequal treatment duration of follow-up between participants.

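### Pregnancy-outcome SAEs dated after the end of participation, chiefly stillbirths and anomalies found near delivery, fall outside the SAP's SAE counts

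*Protocol*

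**What the plan says.** **Status of the outcomes.** Protocol 8.3.4: "Abnormal pregnancy outcomes (for example, spontaneous abortion, fetal death, stillbirth, congenital anomalies, and ectopic pregnancy) are considered SAEs". Protocol 8.3 also lists a congenital anomaly or birth defect among the general SAE criteria.

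**Follow-up of the pregnancy.** Protocol Appendix 4 (10.4), on female participants: "The participant will be followed to determine the outcome of the pregnancy", and on its length: "Generally, follow-up will not be required for longer than 6 to 8 weeks beyond the estimated delivery date".

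**Withdrawal.** Protocol 7.2: "Female participants will be withdrawn from the study if the participant becomes pregnant". Appendix 4 repeats it: "Any female participant who becomes pregnant while participating in the study will discontinue study intervention and be withdrawn from the study".

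**End of participation in the SAP.** SAP 6.2: "End of study participation for a participant will be the earliest of date of death, date of withdrawal from further participation in the study", or the date of Visit 801 or 802. It continues: "Participant data included in the database after the last date of study participation (including safety follow-up period) will be excluded from statistical analysis".

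**Safety event window.** SAP 6.14: "All events that occur between the first dose date of study drug and the end date of study participation will be included".

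The SAP has no pregnancy section, table, listing or exception. Pregnancy appears neither among the special safety topics in 6.14.3 nor in the search criteria of SAP Appendix 3.

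**The concern.** Each rule is ordinary taken alone. Together, the protocol collects pregnancy outcomes after a withdrawal that it requires, and the SAP discards what is dated after withdrawal. The outcomes most exposed to this are those that can only be known late: stillbirth, and an anomaly seen at birth.

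The trial may enrol up to 70% women, admits women of childbearing potential, and treats for 72 to 176 weeks. If the plan is followed literally, the SAE counts and percentages by arm omit events that the protocol itself calls SAEs, and nothing in the SAP replaces them with a summary by arm.

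**Working it through.** The documents state no figure to reproduce. The check concerns timing, then scope, then size.

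**1. When the analysis window closes**

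*From the documents:* in the Schedule of Activities, urine pregnancy tests fall 12 weeks apart to Week 72 (0, 12, 24 ... 72) and 13 weeks apart afterwards (85, 98 ... 176), with extra tests after a missed period. Safety follow-up is 4 weeks (Visit 801) for those leaving within the first 72 weeks and 17 weeks (Visit 802) for those leaving later.

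*Assumptions, not in the documents:* gestation of 40 weeks; detection at gestational week 4 to about 15; withdrawal at detection; the safety visit timed from the visit at which she leaves.

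| Cut-off used | Formula | Window closes at gestational week |
|---|---|---|
| Withdrawal (literal SAP 6.2) | detection | 4 to 15 |
| Visit 801 | detection + 4 | 8 to 19 |
| Visit 802 | detection + 17 | 21 to 32 |

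Even the latest closing point is 40 - 32 = 8 weeks before term. A term stillbirth, or an anomaly found at a term birth, is outside the window on every row. A miscarriage or ectopic pregnancy may be inside it, especially when the loss is how the pregnancy comes to light or when it precedes the recorded withdrawal date.

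One qualification: Protocol 4.1.1.2.5 times Visit 801 from Visit 21 or 99, or from the early-discontinuation visit when Visit 99 is declined. Bringing a pregnant woman back at Week 72 could push a visit-based window past delivery. That would sit badly with mandatory withdrawal, and the earliest-of rule would still cut at the withdrawal date.

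**2. Which cut-off applies**

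- SAP 6.2 takes the earliest date, so withdrawal closes the window before Visit 801 or 802.
- Protocol 7.2 asks anyone leaving the study early, for any reason, to complete safety follow-up.
- The Safety Analysis Set (SAP 6.1) and the adverse-event window (SAP Table GPHK.6.2) both include the follow-up period.

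These do not fit together cleanly. The mismatch touches every early withdrawal, not only pregnancies.

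**3. Which outputs are affected**

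- SAE counts and percentages (SAP 6.14.1.4) are limited to the postbaseline period, so later outcomes are out.
- The SAE listing in the same section shows treatment and is described as covering all SAEs. It sits under 6.14, whose analyses use the Safety Analysis Set over periods ending with safety follow-up unless otherwise specified. Its scope for later events is unclear.
- Narratives (SAP 6.14.2) are planned for every randomized participant with an SAE and state no cut-off.

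**4. Size**

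A range for *all* abnormal outcomes can be sketched. Inputs from the documents: 2400 x 0.70 = 1680 women at the cap; dropout of 25% by Week 72 and 49% over the longer period; 60% with prediabetes (Protocol 9.2). With exponential dropout, mean person-years are about 1.20 and 2.45, and 0.4 x 1.20 + 0.6 x 2.45 = 1.95.

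Assumed: 40-60% of women of childbearing potential, 0.5-2% pregnancies per year, 15-25% abnormal outcomes.

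- Low: 1680 x 0.4 x 1.95 x 0.005 = 6.6 pregnancies; x 0.15 = 1.0 abnormal outcome.
- High: 1680 x 0.6 x 1.95 x 0.02 = 39.3 pregnancies; x 0.25 = 9.8 abnormal outcomes, about 2.5 per arm.

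This is a ceiling on the loss, not an estimate of it, because outcomes inside the window have not been subtracted. Inclusion criterion 4 requires two forms of contraception for sexually active women of childbearing potential, which argues for the low end.

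**The case against.** The strongest reply is that little is lost and nothing is hidden. Early losses and ectopic pregnancies dated on or before the end of participation are counted. Protocol 8.3 sends every pregnancy through the SAE reporting process to collect its outcome, and Appendix 4 provides for reporting related SAEs that arise after the study. The exclusion in SAP 6.2 is worded for statistical analysis, while the SAE listing and narratives carry no explicit cut-off. SAP 6.2 allows additional analyses, and the revision history aligns the special safety topics with a program safety analysis plan that is not available here and might cover pregnancy. With so few events, a table adds little to a listing.

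Much of this stands. The sponsor will hold the information, and a listing may be enough. It does not restore late outcomes to the SAE counts, which stop at the end of participation on any reading in the timing table. Narratives give no counts or denominators by arm. An unseen program-level plan and a general permission for extra analyses do not commit this SAP to anything.

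**Conclusion.** The point holds for SAEs from participants' pregnancies that are dated after the end of participation. Following the SAP as written leaves these out of the SAE counts, and the SAP does not say whether the listing and narratives pick them up. For term outcomes this rests on the stated rules plus the assumptions of a 40-week gestation, detection by about week 15, and withdrawal at detection.

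A reader might infer more, and the documents do not support it:

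- *That all abnormal pregnancy outcomes are dropped.* No rule places every outcome after withdrawal, and those on or before it are counted.
- *That the trial cannot report these outcomes by arm.* The SAE listing includes treatment, and neither it nor the narratives are expressly cut off.
- *That up to about 10 SAEs would be lost.* That figure covers all abnormal outcomes and depends on rates absent from the documents.
- *That partner pregnancies are lost in the same way.* The withdrawal rule applies to female participants only.

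The number lost cannot be derived from the documents and is probably a few events at most. The primary efficacy analysis is unaffected. The omission still matters because these are protocol-defined SAEs, and the correction is cheap.

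**What to change.** - In SAP 6.2 and 6.14, exempt from the end-of-participation cut-off the outcomes of participants' pregnancies that began during study participation.
- Report all of these by randomized arm in one pregnancy-outcome listing or small table, with events after participation identified separately and partner pregnancies listed apart.
- State in SAP 6.14.1.4 and 6.14.2 that the SAE listing and narratives include them.
- Reconcile the earliest-of rule in SAP 6.2 with the safety follow-up in Protocol 7.2, SAP 6.1 and SAP Table GPHK.6.2, so that the closing date for an early withdrawal is unambiguous.

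The withdrawal rule is left as it is, and no new data collection is needed. The cost is a few SAP sentences and one extra output. Some outcomes will arrive after the primary lock and would be reported at the final lock.

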8.3.5. Medical Device Incidents (Including Malfunctions)

Medical devices are being used in this study for the purposes of administering tirzepatide. In order to fulfill regulatory reporting obligations worldwide, the investigator is responsible for the detection and documentation of events meeting the definitions of incident or malfunction that occur during the study with such devices.

The definition of a medical device incident can be found in Section 10.6 (Appendix 6).

Note: Incidents fulfilling the definition of an AE/SAE will also follow the processes outlined in Section 8.3.2.

8.3.5.1. Time Period for Detecting Medical Device Incidents

- Medical device incidents, or malfunctions of the device that result in an incident, will be detected, documented, and reported to the Sponsor during all periods of the study in which the medical device is used.
- If the investigator learns of any incident at any time after a participant has been discharged from the study, and such incident is considered reasonably related to a medical device used during the study, the investigator will promptly notify the Sponsor through the complaints process.

The method of documenting medical device incidents is provided in Section 10.6 (Appendix 6).

8.3.5.2. Follow-up of Medical Device Incidents

- All medical device incidents involving an AE will be followed and reported in the same manner as other AEs (see Section 8.3.2). This applies to all participants, including those who discontinue study intervention.

- The investigator is responsible for ensuring that follow-up includes any supplemental investigations as indicated to elucidate the nature and/or causality of the incident.
- New or updated information will be recorded on the originally completed form with all changes signed and dated by the investigator.

8.3.5.3. Prompt Reporting of Medical Device Incidents and Malfunctions to Sponsor

- Medical device incidents or malfunctions will be reported to the Sponsor within a business day or as determined for the study, after the investigator determines that the event or issue meets the protocol definition of a medical device incident or malfunction.
- Medical device incidents or malfunctions that result in an SAE will be reported to the Sponsor within 24 hours, in the same manner as other (S)AEs.
- Malfunctions will be reported via the Product Complaint Form and sent to the Sponsor per training and per instructions provided on the Product Complaint Form.
- The same individual at the site will be the contact for the receipt of medical device reports and SAE.

